patients will be enrolled. As this is a competitive enrollment study, MUSC will enroll up to 75 volunteers. Eligibility will be determined by each site PI. The PI or Co-I will explain the study to qualified subjects prior to obtaining consent. The subject will also be given an opportunity to review and sign documentation of HIPAA compliance and authorization.

Inclusion criteria:

Patients to be included for participation in this study are:

- 1) Patients with a solid lung lesion 1.5-5cm identified on chest CT (obtained within previous 3 months) with the intention to undergo bronchoscopic evaluation. If the lesion is partially solid (i.e. there is a ground glass component) then the solid portion must make up >75% of the lesion and measure at 1.5-5cm. The decision to pursue biopsy will be made by the treating physician and agreed upon by the patient. This will include patients determined to have an intermediate risk of malignancy (5-65%) and those non-surgical candidate with higher risk lesions in need of diagnosis for alternative treatment. OR
- 2) Patients with a solid lung lesion 1.5-5cm identified on chest CT (obtained within previous 3 months) that are surgical candidates with a high probability of cancer (>65%) will be referred for surgical evaluation. If the lesion is partially solid (i.e. there is a ground glass component) then the solid portion must make up >75% of the lesion and measure at 1.5-5cm. If the patient refuses surgery or if the surgeon requests a definitive diagnosis prior to surgery the patient will have the option to be included in this study. All sites will use the same online calculator to document probability of malignancy.
- 3) Patients whose targeted lung lesion is visualized with fluoroscopy
- 4) Are at least 22 years old,
- 5) Lack Bleeding disorders, and
- 6) Are able to provide informed consent.

Race and gender inclusion will reflect the population characteristics found in the respective regions.

Exclusion criteria:

Patients to be excluded from participation in this study are:

- 1) Patients with a pure ground-glass opacity identified on chest CT
- 2) Patients with endobronchial involvement seen on chest CT.
- 3) Patients who refuse to participate,
- 4) Are less than 22 years of age,
- 5) Lack fitness to undergo flexible bronchoscopy as determined by the bronchoscopist prior to procedure, and
- 6) Are unable to provide informed consent
- 7) Pregnant

INFORMED CONSENT:

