Informed consent will take place in a private environment (e.g. patient exam room), free from distractions. The PI or sub-PI will approach the subject at their standard of care clinic appointment or prior to their scheduled bronchoscopy and will explain the study to qualified subjects prior to obtaining consent. All individuals who obtain consent (PI, Co-I, and study coordinators) have completion certificates for the CITI Human Subjects Research Education Course. Interviews to obtain consent will not follow any stressful situation (e.g. patient being informed he/she may have cancer) and will not be conducted if patient has received any mind-altering medications or anesthesia. Patients will be assessed for their capacity to consent by the ability to show comprehension of the procedure, ask appropriate questions, and appear properly oriented. A signed copy of all consents and the HIPAA authorization document will also be given to consenting subjects.

SUBJECT RANDOMIZATION

Once informed consent is obtained, the site PI will open the next randomization envelope to reveal the assigned procedure. Randomization envelopes are provided by MUSC and are to be opened in order, as indicated by the numbering on the exterior of the envelope. Inside each envelope is the randomization assignment for that subject. The randomization schedule is determined in advance by a computer with the plan for 1:1 randomization overall.

BRONCHOSCOPY PROCEDURES:

Patients will be randomized in a 1:1 fashion (107 in each arm) to undergo (1) standard FOB with fluoroscopy, or (2) R-EBUS with ultrathin bronchoscope (4.2 mm outer diameter with a 2 mm working channel) and guide sheath. This sample size will provide 85% power to detect a 20% improvement in yield using R-EBUS with fluoroscopy. This assumes a diagnostic yield for standard FB with fluoroscopy of 50% and R-EBUS with fluoroscopy is 70%. This also assumes 2-sided hypothesis testing and an alpha level (i.e. significance level) of 0.05. If subjects have multiple pulmonary lesions, it will be predetermined which lesion will be targeted. After informed consent and randomization have been performed, the following will occur:

(1) *Prior to bronchoscopy:* CT images will be obtained within 3 months of bronchoscopy and readily available for viewing during the bronchoscopic procedure. A de-identified copy of the CT and/or PET/CT report will be sent to the coordinating site (MUSC).

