The radiographic information collected will include location of the lesion, size of the lesion, distance from a visible bronchus, and PET characteristics. For R-EBUS procedures, a jpeg ultrasound image of the lesion will be recorded, anonymized, and uploaded to the REDCap study data collection instrument. The location of the lesion (side, lobe and segment, i.e. right upper lobe anterior segment, etc.) will be determined and recorded. The size of the lesion in longest axis diameter will be measured and recorded. The distance from the trachea as calculated as the number of generations from the main carina (first generation) to the lesion will be recorded. All central and peripheral lesions considered intermediate risk will be included. If the patient has undergone a PET, the metabolic activity (measured SUV) will be recorded.

(2) Procedural Characteristics:

The procedural information will include the number of biopsy passes, types of biopsy performed (TBBx, , brush, BAL), and R-EBUS description of site of biopsy of the lesion (within vs. adjacent to) will be recorded. The time length of procedure, type and amount of sedation administered will also be recorded.

(3) Diagnostic Yield and Crossover Procedures:

Primary outcome of diagnostic yield will be determined from the results of the bronchoscopy. A biopsy that results in a specific diagnosis, either malignant or benign, will be assumed to be a true positive. Plan for further diagnostic management for patients who have a non-diagnostic biopsy (and/or biopsy indicating chronic inflammation) will be determined by the attending physician. Those patients will be followed for up to one year until a definitive diagnosis has been made (such as from

surgical pathology), or the lesion has decreased on repeat CT imaging. Under standard procedure randomization, if ROSE indicates chronic inflammation, crossover to R-EBUS will take place.

(4) Confirmation of Diagnosis:

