Confirmation of the diagnosis by surgery or repeat imaging will be recorded for those patients who have non-diagnostic results (including chronic inflammation) from the study procedures. If the patient is referred for surgery, the surgical pathology will be considered the final diagnosis. If the patient has follow-up imaging that shows resolution of the lesion, the lesion will be determined to be of benign etiology. To verify final diagnosis, a copy of the final pathology report from bronchoscopy and any pathology reports from subsequent surgical resection, will be de-identified and provided by the site to the coordinating center.

(5) Complications:

Adverse event rates will be documented. Pneumothorax will be documented by post-biopsy CXR or chest ultrasonography, and the number requiring intervention, such as chest tube placement, will be recorded. Significant hemoptysis will be defined as bleeding noted at the time of procedure that requires a change in the level of care (e.g. outpatient to inpatient or inpatient to ICU) or a blood transfusion. Other adverse events that are common to bronchoscopy described above in "Risks" section will be monitored and reported by the patient or nursing staff.

DATA SAFETY MONITORING PLAN

All subjects enrolled in the trial will undergo routine standard of care bronchoscopy that is indicated a medically necessary by their physicians. Prior to the bronchoscopic procedure, PIs will explain the risks associated with bronchoscopy, and verify that the research only risks have been explained, and that the subject has signed an informed consent form. There are no anticipated risks, outside of the risk for the standard of care procedures for this clinical trial. All subjects are required to read, understand, and sign the informed consent form associated with the research study. Each subject will be informed of post procedure symptoms of which to be aware that may represent adverse reactions to the bronchoscopy. Symptoms that the patient will be informed to look out for include:

- Pain or difficulty with swallowing
- Difficulty breathing
- Vomiting
- Dizziness
- Abdominal or chest pain
- Continuous bright red blood in your sputum
- Fever above 100.0 degrees Fahrenheit

If the subject notes any of these symptoms, he/she is instructed to contact his/her physician, who will determine the course of action. All events are to be reported within 48 hours of occurrence to the coordinating site (MUSC). All adverse events (AEs) will

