Each site investigator will review the results, and the results will become part of the subject's medical record and research record. Any clinical follow-up or repeat procedures will be dictated by the patient's physician based on clinically relevant data and will not be influenced by enrollment into this study. To protect subject

confidentiality, MUSC will receive all sites' data as de-identified through use of the 6 digit patient codes. All information and data related to this study will be stored in a secured, locked cabinet in MUSC Clinical Sciences Building Room 809. The privacy of subjects will be protected using a 6 digit computer generated random code. The key to the code will be kept in a password protected folder on the MUSC DB2 (\DA) server; access to this folder is restricted to study personnel alone.

Electronic Data will be entered and stored in the secure REDCap database created for this study. REDCap is a web-based application designed exclusively to support data capture for research studies. It provides an intuitive interface for data entry, audit trails for tracking data manipulation and export procedures, procedures for importing data from external sources, advanced features such as branching logic and calculated fields, and automated export procedures for seamless data downloads to common statistical packages such as SPSS, SAS, Stata, and R. It was developed at Vanderbilt University (see <http://redcap.vanderbilt.edu/consortium/index.php>) and is ideal for remote data entry, as will be the case for this multi-center trial.

III. STATISTICAL ANALYSIS:

Statistical comparisons will be made using chi-square analysis where applicable. Sensitivity, specificity, positive and negative predictive value and accuracy of all procedures will be calculated. A logistic regression analysis of factors influencing tissue quantity will be undertaken.

Coordinating Center: MUSC will be the designated coordinating center for this trial. MUSC will be responsible for development of the database, housing the data, working with the sites on IRB issues, patient enrollment, completion of on-line data collection instrument and validation of the data. MUSC will also be responsible for payment to the sites when a patient's case report form is complete and query-free. Statistical support and interim analysis will be performed at MUSC by an in house statistician ([name]). Interim results will be shared with all participating sites during teleconference meetings.

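### If the rule that every specific biopsy result is a true positive also fills the accuracy table, PPV and specificity are fixed in advance, and the plan does not clearly let resection pathology override it

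*Combined protocol and SAP*

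**What the plan says.** All references are to the combined protocol and SAP.

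- **DATA COLLECTION (3), Diagnostic Yield and Crossover Procedures.** "Primary outcome of diagnostic yield will be determined from the results of the bronchoscopy". The next sentence gives the only rule that classifies a bronchoscopy result: "A biopsy that results in a specific diagnosis, either malignant or benign, will be assumed to be a true positive". Non-diagnostic patients are followed for at most a year, until there is a definitive diagnosis or the lesion has become smaller on CT.
- **DATA COLLECTION (4), Confirmation of Diagnosis.** It opens: "Confirmation of the diagnosis by surgery or repeat imaging will be recorded for those patients who have non-diagnostic results". It continues: "If the patient is referred for surgery, the surgical pathology will be considered the final diagnosis". Follow-up imaging gives a benign label when the lesion has resolved. Sites send documents to the coordinating center: "To verify final diagnosis, a copy of the final pathology report from bronchoscopy and any pathology reports from subsequent surgical resection".
- **Section III, Statistical Analysis.** "Sensitivity, specificity, positive and negative predictive value and accuracy of all procedures will be calculated". No target condition, test-positive rule or true-negative rule is given there or elsewhere.
- **Inclusion criteria.** Criterion 2 admits some surgical candidates: "if the surgeon requests a definitive diagnosis prior to surgery the patient will have the option to be included in this study". Criterion 1 admits non-surgical candidates with higher-risk lesions.
- **Section II, Primary and Secondary Outcomes.** Yield is primary. The five accuracy measures appear in neither list.

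**The concern.** PPV and specificity measure how often a positive result is wrong. A rule that declares every specific result correct removes the only cell that could show this. The trial could then report 100% for both, with a confidence interval, although nothing had been estimated.

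The table is also unclear in itself. A specific benign result counts as positive, yet a non-diagnostic lesion that resolves is labelled benign. Benign disease therefore sits on both sides, and what counts as a true negative is not stated. The analyst would have to settle this after seeing the data.

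Some specific results will have a later resection report, because patients biopsied ahead of surgery are eligible. The plan does not say plainly what happens when the two reports disagree.

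**Working it through.** **Inputs.** 107 patients per arm, yields of 50% (standard) and 70% (R-EBUS), two-sided alpha 0.05 and 85% power, all from BRONCHOSCOPY PROCEDURES. The documents give no rate of wrong specific results, no share of patients resected and no count of true negatives.

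**1. The plan's own figure.** With pooled variance and no continuity correction, n = [1.960·√(2·0.6·0.4) + 1.036·√(0.5·0.5 + 0.7·0.3)]² / 0.20² = 106.2, so 107 per arm. Power at 107 is 85.3%. The stated sample size reproduces, and it does not use the accuracy measures.

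**2. How many results the rule touches.** Expected specific results are 107 × 0.50 = 53.5 and 107 × 0.70 = 74.9. Expected non-diagnostic results are 53.5 and 32.1.

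**3. The table if the yield rule governs and resection does not override.** FP = 0.
- PPV = TP/(TP + FP) = TP/TP = 100%.
- Specificity = TN/(TN + FP) = TN/TN = 100% if any true negative exists, otherwise 0/0.

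Neither depends on the data. An exact 95% interval would still look informative: its lower limit is 0.025^(1/n), which is 93.3% for 53 of 53 and 95.2% for 75 of 75.

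**4. What the rule could hide (assumed values).** Keep any specific result as test-positive and suppose a share e of them is wrong. PPV is then 1 − e, so 99% to 90% for e of 1% to 10%. At e = 5%, FP is 53.5 × 0.05 = 2.7 and 74.9 × 0.05 = 3.7.

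| Assumed TN per arm | Specificity, standard | Specificity, R-EBUS |
|---|---|---|
| 5 | 65% | 57% |
| 10 | 79% | 73% |
| 20 | 88% | 84% |

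These figures show how far specificity can depart from 100% when few results are wrong. They are not predictions and do not compare the arms.

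**5. The table if resection does override.** Let r be the share of specific results that are resected. Unresected ones still count as correct, so FP can be at most r times the specific results, and PPV over all of them cannot fall below 1 − r however often the biopsy errs. Verification is partial and selected, because non-surgical candidates are eligible but are not expected to be resected.

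**6. The target condition.** If the target is malignancy, a specific benign result cannot be a true positive. If the target is any diagnosable lesion, a non-diagnostic lesion later called benign looks like a miss, and it is unclear who could be a true negative. Neither choice fits all the stated rules.

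**7. The imaging reference, a separate gap.** Follow-up may stop when a lesion has shrunk, but the benign label from imaging requires that it has resolved. A lesion that shrank without resolving, or is stable at one year, has no reference result unless tissue was obtained. Such patients would come from the expected 53.5 and 32.1 non-diagnostic results. How many there would be cannot be derived from the documents.

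**The case against.** The strongest reply is that the two data-collection sections work together: a specific result is presumed correct unless surgery provides the final diagnosis. The sentence on surgical pathology carries no limit of its own, and collecting resection reports to verify the diagnosis would make little sense if they could change nothing. In addition, the true-positive sentence stands in the yield paragraph, and the statistical section never says that it fills the accuracy table.

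Much of this stands. A reader might infer that the plan fixes PPV and specificity at 100%. The documents do not support that flatly, because it needs both the transfer of the yield rule and the absence of an override. What remains is that the confirmation section opens with non-diagnostic patients, never mentions reclassifying a specific result, and is not reconciled with the yield rule. The override reading also leaves verification partial.

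A reader might also infer that the primary comparison is compromised. It is not: yield is taken from the bronchoscopy result, so it compares how often a specific result is obtained. A wrong specific result would count as a success. At an equal assumed error rate e in both arms, the planned 20-point gap would be 20(1 − e) points in correct diagnoses, or 19.8 to 18.0 for e of 1% to 10%.

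Finally, a reader might want to quantify how far the choice of table moves sensitivity, NPV or the accuracy gap. The documents do not give the benign shares this needs. Assuming the same benign share among non-diagnostic lesions in both arms can also imply different malignancy prevalence in randomized groups. No such figures are offered.

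**Conclusion.** The point holds in conditional form, with moderate confidence. If the yield rule fills the accuracy table and resection does not override it, PPV is 100% and specificity is 100% or undefined, for about 54 and 75 expected specific results, regardless of the data. If resection does override, both measures still rest on an assumption for every unresected specific result. On either reading the target condition and the true-negative cell lack a consistent meaning, so the table needs defining.

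The consequence is limited to measures that are neither primary nor secondary outcomes. The expected counts rest on the planning yields, and the error rates and true-negative counts above are assumptions. This should be corrected before analysis, but it does not threaten the main result.

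**What to change.** 1. State that diagnostic yield means a specific result was obtained.
2. Name one target condition for the accuracy measures and define all four cells. With malignancy as the target, for example, a specific benign result is test-negative. State where a non-diagnostic result falls.
3. State that resection pathology already collected overrides the bronchoscopy result for these measures, and show unresected specific results as a labelled assumption.
4. Drop PPV and specificity, or report them only in resected patients, labelled as a selected subset with partial verification.
5. Separately, reconcile shrinkage and resolution as the imaging reference. Report the number of unresolved non-diagnostic patients per arm, and give sensitivity and NPV with all of them malignant and with all of them benign.

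The cost is protocol and analysis wording, using data already planned, with no new visits or tests. The drawback is that PPV and specificity are lost or become less precise and apply only to a selected group. Sensitivity and NPV become ranges that still depend on the labelled assumption.

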Despite new technologies that have arisen in the last decade for bronchoscopic biopsy of peripheral pulmonary lesions, the sensitivity for FOB remains as low as 34% for lesions < 2cm and increases to around 63% for lesions >2cm in size, but decreases again as the distance from the hilum increases. The use of R-EBUS as an adjunct is recommended as it increases diagnostic yield. A biopsy approach using R-EBUS through an ultrathin scope, guide sheath and fluoroscopy may increase the diagnostic yield of pulmonary lesions even further when compared to standard FB with fluoroscopy; it may also improve the utility of bronchoscopy for the diagnosis of peripheral pulmonary lesions thereby decreasing the need and risk associated with TTNA. This study will also evaluate the radiographic and procedural factors that have been described to influence that diagnostic yield.

II. RESEARCH DESIGN AND METHODS

This is a multi-center, prospective, randomized controlled trial to evaluate the diagnostic yield of two standard of care bronchoscopy procedures used to biopsy peripheral pulmonary lesions identified on chest CT: (1) standard FB using an adult standard bronchoscope (Olympus BF-180) with fluoroscopy, and (2) bronchoscopy using the BFP-190 ultrathin bronchoscope in combination with R-EBUS and guide sheath.

Primary outcomes: Diagnostic yield of standard FB with fluoroscopy using standard adult bronchoscope versus bronchoscopy using ultrathin bronchoscope in combination with R-EBUS with or without guide sheath for lung lesions 1.5-5 cm.

Secondary Outcomes:

- 1) The radiographic and procedural factors that influence the diagnostic yield including the size and location of the lesion, the distance from the main carina, the number and type of specimens obtained, and the location of sampling within the lesion.
- 2) Adverse event rates of hemoptysis and pneumothorax.

DEFINITIONS:

Lung lesions: solid nodules or masses 1.5-5 cm in diameter

SUBJECT ENROLLMENT (See Figure 1):

Subjects presenting to their standard of care pulmonologist in need of a bronchoscopic biopsy of their peripheral pulmonary lesion as part of their standard medical care, and who meet study inclusion/exclusion criteria, will be invited to participate. A total of 214

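### Study follow-up of a non-diagnostic patient may end on any CT decrease, with no minimum change or confirming scan, while only resolution counts as benign, so measurement noise can close cases without a final status.

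*Combined protocol and SAP*

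**What the plan says.** Data Collection (3), Diagnostic Yield and Crossover Procedures, covers patients whose biopsy is non-diagnostic or shows chronic inflammation. It limits their follow-up to one year and names two events that end it sooner. One is a definitive diagnosis, for which surgical pathology is the example given. The other rests on imaging alone: "or the lesion has decreased on repeat CT imaging". No section gives a minimum decrease, a scan schedule, an allowance for measurement error, a reader rule or a confirming scan.

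The size measure is under Data Collection (1): "The size of the lesion in longest axis diameter will be measured and recorded". The Definitions admit "solid nodules or masses 1.5-5 cm in diameter".

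Data Collection (4), Confirmation of Diagnosis, uses a stricter term: "If the patient has follow-up imaging that shows resolution of the lesion, the lesion will be determined to be of benign etiology". It also asks sites for the bronchoscopy pathology report and for reports from any later surgical resection. Needle-biopsy reports are not named.

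Section III commits to the analyses that need a final diagnosis: "Sensitivity, specificity, positive and negative predictive value and accuracy of all procedures will be calculated". The primary outcome does not need one: "Primary outcome of diagnostic yield will be determined from the results of the bronchoscopy".

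**The concern.** The natural reference for a decrease is the patient's own entry CT, so the literal threshold is zero change. An unchanged lesion is then as likely to read smaller as larger, and a reading 1 mm below entry ends study follow-up.

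Specific diagnoses are assumed to be true positives, so follow-up of non-diagnostic patients is the plan's route to its false negatives. If it closes on noise, two things go wrong. The lesion has neither a definitive diagnosis nor resolution, so its place in the accuracy table is undefined. And if it is a cancer that later declares itself and is proven by needle biopsy, nothing obliges the site to report it. Missing false negatives push sensitivity up and make NPV unreliable.

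**Working it through.** **1. The plan's own figure.** The plan gives no figure for the follow-up rule; its sample size is the nearest. For 50% versus 70%, two-sided alpha 0.05 and 107 per arm, with pooled variance under the null (mean 0.60):

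Φ{[0.20 − 1.96·√(2·0.6·0.4/107)] / √[(0.25 + 0.21)/107]} = 85.3%.

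The stated 85% reproduces. The same yields imply about 107 × 0.50 + 107 × 0.30 ≈ 54 + 32 = 86 non-diagnostic patients entering this rule, before any crossover.

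**2. Unchanged lesions without rounding.** No measurement SD is needed. At one scan, P(reading below entry) = 1/2. Over three scans against one entry reading, the chance of at least one lower reading is 1 − P(entry is the smallest of four) = 1 − 1/4 = 75%. Lower figures arise only from ties when readings are rounded.

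**3. Rounded readings and growth.** The documents give no measurement error, scan dates or growth rates, so these are assumptions: reading SD 0.5, 1.0 or 1.5 mm; readings to the nearest mm; scans at 90, 180 and 365 days; true diameter d·2^(t/(3·VDT)), where VDT is the volume doubling time; entry diameter d plus uniform ±0.5 mm; 400,000 simulated lesions per setting. A decrease is any follow-up reading below the entry reading.

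| Lesion | One or more of three scans reads smaller (SD 0.5 / 1.0 / 1.5 mm) |
|---|---|
| Unchanged, 20 mm | 45% / 60% / 66% |
| 15 mm, VDT 400 days | 5% / 22% / 34% |
| 20 mm, VDT 400 days | 2% / 15% / 28% |
| 30 mm, VDT 400 days | 0.3% / 8% / 18% |
| 20 mm, VDT 200 days | 0% / 3% / 11% |

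At the first scan alone, an unchanged 20 mm lesion reads smaller in 26%, 37% and 41%.

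**4. Effect on sensitivity.** Assume that the malignant fraction is equal in diagnosed and non-diagnosed patients, so that true sensitivity equals the planned yield Y, and ignore crossover. Let s be the share of missed cancers under CT surveillance alone and L the share of those closed by noise and never recorded. Then

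observed sensitivity = Y / [Y + (1 − Y)(1 − sL)].

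With the 20 mm, 400-day rates (L from 0.02 to 0.28):

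- s = 1, L = 0.28: 0.50/(0.50 + 0.50·0.72) = 58.1%, and 0.70/(0.70 + 0.30·0.72) = 76.4%. The difference is 18.3 points instead of 20.
- s = 1, L = 0.02: 50.5% and 70.4%, difference 19.9.
- s = 0.3 (assumed), L = 0.28: sL = 0.084, giving 52.2% and 71.8%, difference 19.6.

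The upward shift is therefore about 0–2 points at s = 0.3 and about 8 points at the extreme of these settings. The between-arm difference moves by less than 2 points.

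**5. Crossover.** Bronchoscopy Procedures (6) sends standard-arm patients with a non-diagnostic ROSE to the ultrathin scope with R-EBUS. If all standard-arm failures cross over with crossover yield y, the share reaching the CT rule is 50% × (1 − y): 40%, 30%, 25% or 15% at y = 20%, 40%, 50% or 70%. The R-EBUS arm has 30%. The arms are equal at y = 40%, and above that the imbalance reverses.

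**The case against.** The strongest reply is that little rests on this rule. Needle aspiration and surgery are listed beside follow-up CT as next steps, any later resection pathology is collected, and clinical follow-up is "based on clinically relevant data and will not be influenced by enrollment into this study". The cancers exposed are those under surveillance only, growing slowly, misread as smaller, and later proven without resection. That stands, and it is why the likely bias is small. It does not remove the gap, because nothing tells the study to keep recording after the stop.

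A second reply is that *decreased* need not mean a 1 mm subtraction: readers may call small changes stable. That is plausible. Ignoring changes under 2 mm, noise would still close 1–43% of unchanged lesions over three scans, with an SD of 0.5 to 2.0 mm for the difference between two readings. Such a convention would need to be written down.

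A reader might infer that the standard arm loses more of its missed cancers because 50% rather than 30% are non-diagnostic. The documents do not support that: with crossover the imbalance at the CT rule is not established and could reverse. A reader might also infer that a decreased lesion is labelled benign. It is not, since Data Collection (4) requires resolution; its status is simply undefined. For the same reason, the upward bias in sensitivity is conditional on such cases dropping out of the false-negative count.

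**Conclusion.** The point holds as a defect in the reference standard for secondary accuracy measures. The wording is certain: no minimum change, no confirmation, and two different imaging criteria in adjacent sections. That many unchanged lesions would be closed under a literal reading follows from symmetry. The rate for missed cancers, about 0–34% across 15 to 30 mm at a 400-day doubling time, rests on assumed measurement error, scan dates and growth. It is near zero with low noise and larger or faster-growing lesions.

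The sensitivity bias of 0–2 points, or about 8 at the extreme, also rests on the assumed share under surveillance, on the 20 mm loss rates and on ignoring crossover. No direction of between-arm distortion is established. The primary yield comparison and its power are unaffected. The change is worth making because it is cheap, not because the trial's main conclusion depends on it.

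**What to change.** In Data Collection (3), keep recording study outcomes from the chart, including any needle-biopsy pathology, to the planned one year for every non-diagnostic patient, unless a definitive diagnosis or resolution is documented first. Use the same imaging term there and in Data Collection (4), and state how a lesion that is smaller but unresolved at one year enters the accuracy analyses.

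This needs no threshold. If an early stop for shrinkage is kept, it should require a prespecified decrease beyond measurement error. As an illustration only, a fall of at least 2 mm seen again on the next scan would cut noise closures of unchanged lesions to 0.1–15%, from 35–65% under the current wording (1 mm readings, SD of the difference 0.5 to 2.0 mm).

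The change governs study data recording only; clinical imaging stays with the treating physician. The cost is a sentence or two in the protocol, matching case report form guidance, and somewhat longer chart abstraction within the year already planned. No scans are added, and the sample size does not change.
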